	To demonstrate that morning injection of Toujeo compared to Lantus will provide better glycemic control evaluated by Continuous Glucose Monitoring (CGM) in adult patients with type 1 diabetes mellitus.
	Secondary objective(s):
	To demonstrate that treatment with Toujeo compared to Lantus will provide
	 lower incidence rate of nocturnal symptomatic hypoglycemia, better glucose control coverage during the last hours of CGM before next basal-insulin dosing; less variability in CGM profile.
STUDY DESIGN	A multicenter, randomized, active-controlled, parallel group, 16-week openlabel study. The study consists of an up to 4-week screening and CGM training period and a 16-week treatment period. Blinded CGM data (blinded to both patients and investigators) will be collected at the end of screening (Week -2 to 0) and the end of treatment (Week 15-16) for endpoint analyses.
	During the baseline training period, patients will wear a blinded CGM device for 7 consecutive days to generate a minimum 4 days of usable CGM data to be eligible for randomization. If a patient fails the first attempt for any reason, he/she will be retrained for CGM conduct and complete another course of blinded CGM.
	Patients satisfying the inclusion/exclusion criteria and CGM requirements will be randomized 1: 1 to morning injection of either Toujeo or Lantus. Given the potential impact of certain variables on the primary endpoint, randomization will be stratified by baseline HbA1c (<8, ≥8), frequency of the basal insulin injections at screening BID vs QD, current CGM use (yes/no) and mealtime insulin titration algorithm followed.
	Dosing will be once daily in the morning, defined as the time period between waking up and breakfast. The injection time will be discussed between the investigators and patients at randomization and should be kept consistent at the same time each day. The patients will also be asked to maintain a log of the time of injection.
	During the entire study starting after screening, patients will perform Self-Monitoring of Plasma Glucose (SMPG) as specified in the study flow-chart and the protocol. SMPG readings will be used to guide insulin dose-titration for optimal glycemic control and the SMPG profiles will be collected for efficacy analyses.
	Appropriate dose titration of basal and mealtime insulin will be implemented

02-Aug-2016 Version number: 1

as outlined in the dose regimen section. Titration of basal insulin will be allowed until Week14 of the study after which, the Toujeo/Lantus dose should remain unchanged during the period of the CGM collection (Week 15 or 16), while meal-time insulin dose can still be adjusted as appropriate.

During Week15, patients will wear a blinded CGM device for 7 consecutive days to generate a minimum of 4 days of useable CGM data. If a patient fails the first attempt for any reason, he/she will be retrained for CGM conduct and complete another week of blinded CGM data collection during Week 16.

At the end of the study, the patients will be followed-up within 2 (+2) days to collect post treatment safety information.

STUDY POPULATION

Main selection criteria

Inclusion criteria:

- Adult patients (male and female) with type 1 diabetes mellitus
- Signed written informed consent

Exclusion criteria:

- Age <18 years or >70 years;
- Fasting c-peptide ≥0.3nmol/l as per source document or central lab test at Visit 1.
- HbA1c ≤6.5% or ≥10.0% via central lab test at Visit 1,
- Patients who experienced none episode of documented symptomatic and/or severe hypoglycemia (as per the ADA classification) during the past month prior to screening,
- Patients who experienced >1 episode of severe hypoglycemia resulting in coma/seizures during the last 12 months before screening,
- Patients receiving less than 1 year treatment with basal plus mealtime insulin,
- Using any basal insulins other than long acting-insulin analogs (i.e. Lantus, Toujeo, Levemir or Tresiba) in the past 3 months before screening,
- Requiring >80 U/day basal insulin analogs and/or not on stable dose (± 20% total dose) within 30 days prior to screening,
- Using fewer than 2 injections of rapid-acting insulin analog per day within 30 days prior to screening,
- Using human regular insulin as mealtime insulin within 30 days prior to screening
- Using an insulin pump during the last 6 months before screening,
- History of unstable proliferative diabetic retinopathy or any other rapidly progressive diabetic retinopathy or macular edema likely to require treatment (eg, laser, surgical treatment or injectable drugs) during the study period,
- Pregnant or breast-feeding women or planning pregnancy during the duration of the study,
- Use of any other investigational drug(s) within 1 month or 5 halflives, whichever is longer prior to screening,
- Inappropriate CGM use during screening period evidenced by failure to obtain a minimum of 4 days of usable records by the end of screening,
- Non-compliance with SMPG performance evidenced by failure to demonstrate at least 5 days of 5-point SMPG records by the end of screening.

Total expected number of patients	Approximately 616 patients randomized, aiming for approximately 524 patients with evaluable data.					
	Approximately 100 study sites.					
STUDY TREATMENT(s)	Tested drug: Toujeo (HOE901-U300)					
(-)	Control drug: Lantus (HOE901-U100)					
Investigational medicinal	,					
product(s)	Testing drug: Toujeo (Insulin glargine -U300)					
Formulation:	Toujeo will be supplied for subcutaneous (SC) injection as a sterile, non-pyrogenic, clear, colorless solution in a 1.5 mL Toujeo SoloStar disposable prefilled pen (450 Units/1.5 mL).					
Formulation:	Application of the drug is done using an injection pen device allowing dose setting in the range of 1-80 U with 1 U increment.					
	Mixing of Toujeo with other insulins is not allowed nor dilution.					
	Control drug: Lantus (Insulin glargine-U100)					
	Lantus will be supplied for SC injection 100 U/mL in 3 mL cartridges assembled in a pen-injector. Lantus SoloStar prefilled (disposable) pen will be used for this study.					
	The disposable SoloStar pen-injector allows for a dose setting in the range 1-80 U with minimum dose increment of 1 U.					
	Mixing of Lantus with other insulins is not allowed nor dilution.					
Route(s) of administration:	Subcutaneous injection.					
Dose regimen:	Toujeo and Lantus will be self-administered by SC injection once daily in the morning, which is defined as the time period between waking up and prebreakfast. The clock time for the morning injection (hh:mm) will be established at the discretion of the patient/investigator at the time of randomization and will be maintained for the duration of the study.					
	 On the randomization day (Day 1), the initiation dose of glargine (Toujeo and Lantus) is the patient's current dose of their basal-insulin analogs. For patients taking the basal insulin in any time other than morning injection previously, they should switch the dosing time to morning injection during screening period. During the treatment period, dose of Toujeo and Lantus) will be titrated in dose steps outlined in the table below to achieve glycemic target and minimize the potential risk of hypoglycemia. The target range for fasting SMPG is 80–100 mg/dL (4.4-5.6 mmol/L). Dose adjustment for insulin glargine is based on the mean fasting (prebreakfast/pre-injection) SMPG values of the last 3 days without related hypoglycemia. For each titration step, the insulin dose increment should not exceed 10% of the existing glargine daily dose, irrespective of the mean fasting SMPG values, eg, for a daily dose of 30 U, the increment should be 3 U if the mean fasting SMPG is >120 mg/dl. Titration of insulin glargine will be continued until the end of Week 14, after which patients will maintain a stable dose during the endpoint for 					
	blinded CGM collection (Weeks 15-16) except for dose reduction in the case of safety reasons (eg, basal insulin related severe hypoglycemia).					

02-Aug-2016	
Version number:	1

Mean fasting SMPG values (last 3 days)	Insulin Glargine (U-100 or U-300) dose adjustments (U/day) ^a
≥120 (> 6.7 mmol/L)	+ 4 Units, or split to 2x2 U
≥100 and ≤120 mg/dL (>5.6 and ≤6.7 mmol/L)	+ 2 Units, or split to 2x1 U
Glycemic target: mean fasting SMPG between 80 – 100 mg/dL 80 and 100 mg/dL (4.4 and 5.6 mmol/L), inclusive	No change
≥60 and <80 mg/dL (≥3.3 and <4.4 mmol/L)	-2 Units
<60 mg/dL (3.3 mmol/L) or occurrence of 2 (or more) symptomatic hypoglycemic episodes or one severe hypoglycemic episode	-4 Units or at the discretion of the investigator or medically qualified designee

^a Prior to additional basal insulin titration, mealtime insulin should be titrated to achieve a bedtime and pre-breakfast glucose delta <50 mg/dL.

Noninvestigational medicinal product(s) (if applicable)

Formulation:

Route(s) of administration:

Dose regimen:

Patients in both treatment groups will continue with their current rapid-acting insulin analog (eg, insulin glulisine, insulin lispro or insulin aspart) during the study.

Solution for subcutaneous injection.

Subcutaneous injection.

- Patients will continue on their existing mealtime insulin (rapid-acting insulin analog) regimen at randomization.
- The injection time and frequency of rapid-acting insulin will be at investigator's discretion in accordance with the prescribing information.
- During the treatment period, the doses of the mealtime insulin analog should be actively titrated to achieve and maintain the 2-hour postprandial SMPG in the range 130-180 mg/dL (7.2-10 mmol/L).
- Dose adjustment of mealtime insulin will be allowed throughout the 16 weeks of treatment period, including the endpoint period for blinded CGM collection (Week 15-6) with the fixed doses of insulin glargine
- Dose adjustment of mealtime insulin can be based on a pattern of postmeal SMPG data from the prior 3 days (simple titration) OR the carbohydrate content of the meal; both the recommended regimens are outlined below

Simple titration: Titration of mealtime insulin based on a pattern of post-meal glucose median 130 </>180 mg/dl in the prior 3 days using the table below

Mealtime dose of Insulin	Pattern of Postprandial BG values <130 mg/dL ^a	Postprandial BG values >180 mg/dL ^a
≤10 Units	Decrease dose by 1 Unit	Increase dose by 1 Unit
≥11-19 Units	Decrease dose by 2 Units	Increase dose by 2 Units
≥20 Units	Decrease dose by 3 Units	Increase dose by 3 Units

 $^{^{\}it a}$ If more than one-half of the mealtime blood glucose (2-hours PPG) values for the week were above target.

OR

Carb counting: (insulin-to-carbohydrate ratio) group

Starting recommendation 1 unit to 15 grams carbs

Consider calculating insulin to carb (I:C) ratio = 500 / total daily dose (TDD) of insulin.

Mealtime dose of Insulin	Pattern of Postprandial BG values <130 mg/dL ^a	Pattern of Postprandial BG values >180 mg/dL ^a
1 unit/20 g	Decrease to 1 unit/25 g	Increase to 1 unit/15 g
1 unit/15 g	Decrease to 1 unit/20 g	Increase to 1 unit/10 g
1 unit/10 g	Decrease to 1 unit/15 g	Increase to 2 unit/15 g
2 unit/15 g	Decrease to 1 unit/10 g	Increase to 3 unit/15 g
3 unit/15 g	Decrease to 2 unit/15 g	Increase to 4 unit/15 g

^a If more than one-half of the mealtime blood glucose values for the prior 3 days were above target.

Correction dose: Investigators will be provided an initial guideline of 1800/TDD as a correction factor, if applicable, in addition to investigator directed change in correction factor based on glucose patterns.

02-Aug-2016 Version number: 1

ENDPOINT(S)

Primary endpoint:

 Percentage (%) of time plasma glucose in target range of 70-180 mg/dL (3.9-10 mmol/L) during Weeks 15-16, obtained from CGM.

Secondary endpoint(s):

- Incidence and rate of nocturnal symptomatic hypoglycemia, defined as an event with typical symptoms of hypoglycemia accompanied by SMPG ≤70 mg/dL (3.9 mmol/L) that occurs between 00:00 and 05.59 hours.
- Percentage (%) of time glucose concentrations obtained by CGM within target range of 70-140 mg/dL (3.9-7.8 mmol/L) during the last 4 hours of CGM data collection prior to next day basal insulin injection.
- Total, within day and between day coefficient of variation in glucose obtained from CGM.

Other endpoints:

- Frequency and distribution (nocturnal or 24 hours) of all hypoglycemia events analyzed by hypoglycemia categories (severe, documented symptomatic, asymptomatic, probable and relative) as defined in the publication ADA Workgroup on Hypoglycemia, 2015.
- Additional CGM Endpoints (data obtained during Week 15-16):
 - Percentage (%) of time glucose concentrations within the target range of 70-140 mg/dL (3.9-7.8 mmol/L) ☐ analyses on all- time (24 hours) CGM data,
 - Percentage (%) of time glucose concentrations ≤70 mg/dL (3.9 mmol/L) and <54 mg/dL (3 mmol/L) ☐ analyses on both all-time (24 hours) and nocturnal (00:00–05:59 hours) CGM data,
 - Percentage (%) of time glucose >140 mg/dL (7.8 mmol/L), >180 mg/dL(10 mmol/L) and > 250 mg/dL (13.9 mmol/l) □ analyses on both all-time (24h) and nocturnal (00:00–05:59 hours) CGM data,
 - Total, within day and between day coefficient of variation in glucose concentrations
 - Area under the glucose curve (AUC) of glucose concentration ≤70 mg/dL (3.9 mmol/L)
 - AUC of glucose concentration >180 mg/dL(10 mmol/L)
- 7-point SMPG profiles (pre-prandial and 2-hour postprandial plasma glucose at breakfast, lunch and dinner, and bedtime);
- Change from baseline to study endpoint in HbA1c
- Change from baseline to treatment endpoint in central lab FPG
- Insulin dose (total, basal, mealtime/bolus, ratio of basal to bolus insulin dose)

Safety:

Evaluation of injection site reactions, hypersensitivity reactions, adverse events, serious adverse events (including hypoglycemic episodes associated with seizures, coma or unconsciousness etc) and vital signs.

ASSESSMENT SCHEDULE The schedule of study-related procedures/assessments is detailed in the Study Flowchart. The study design and visit schedule is detailed in study flowchart Section 1.1. STATISTICAL CONSIDERATIONS Sample size determination: A sample size of 262 evaluable patients per treatment arm would provide at least 90% power to demonstrate superiority of Toujeo over Lantus in the percentage of time plasma glucose within the range of 70-180 mg/dL, using a 2-sided test with an α-level of 0.05. This is assuming an absolute difference of at least 4%, a standard deviation of 14%, and an expected value of 53% in the Lantus arm. This sample size would also provide at least 80% power to demonstrate a difference in the rate of documented symptomatic nocturnal hypoglycemia occurring at any point post randomization, assuming a rate ratio (Toujeo over Lantus) of at most 0.86 events per pt-year. Analysis population: Efficacy analyses will be performed on the modified Intent-to-Treat (mITT) population, which will comprise of all patients who are randomized and who have at least one post-baseline assessment for the endpoint of interest. Safety analyses will be performed on the safety population, which will comprise of all patients who receive at least one dose of study treatment. Primary analysis: The percentage of time glucose in target range 70-180mg/dL (3.9–10mmol/l) during weeks 15-16 (obtained from CGM) will be calculated based from the denominator of total time with valid data. The percentages will be summarized and analyzed for differences between treatment groups using a generalized linear model, adjusting for key baseline characteristics (duration of diabetes, BMI, age and baseline value) and randomization strata. Analysis of secondary endpoints: Continuous CGM endpoints will be analyzed using a generalized linear model as described for the primary endpoint. The change in HbA1c (and FPG) from baseline to endpoint will be analyzed using a mixed-effect model with repeated measures (MMRM) approach under the missing at random framework, using an adequate contrast at endpoint. The model will include fixed categorical effects of treatment arm, visit. treatment-by-visit interaction, randomization strata, and baseline HbA1c as covariate as well as baseline HbA1c-by-visit interaction. Other categorical CGM endpoints will be analyzed using the Chi-square or Cochran-Mantel-Haenszel test, including randomization strata. Fisher's Exact test will be employed if required. The incidence of hypoglycemia will be analyzed using logistic regression, adjusting for randomization strata and other baseline characteristics (duration of diabetes, BMI and age) as clinically appropriate and if the model permits. The rate per patient-year of hypoglycemic events will be analyzed using an over-dispersed Poisson regression model, adjusting for randomization strata

and other baseline characteristics (duration of diabetes, BMI and age) as

clinically appropriate and if the model permits.

DURATION OF STUDY PERIOD (per patient)

[figure not shown]
The study duration consists of:

- Up to 4-week screening and training period including 1-2-week CGM performance (allow for re-training);
- 14-week open-label, comparative treatment period allowing for dose titration in both basal and meal-time insulin;
- 1-2 week blinded CGM collection with fixed dose of Toujeo or Lantus,
- 2 days of post-treatment safety follow-up period after treatment completion or premature discontinuation of study treatment.

The maximum study duration per patient will be around 20 weeks.

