Appropriate dose titration of basal and mealtime insulin will be conducted as specified in Section 8. Titration of basal insulin will be allowed until the end of week 14, after which, Toujeo/Lantus dose should remain unchanged during Week 15-16 for blinded CGM collection, while meal-time insulin dose can still be appropriately adjusted.

During the entire study starting after screening, patients will perform Self-Monitoring of Plasma Glucose (SMPG) which is specified in Section 1.2 and Section 10.2.3. SMPG readings will be

02-Aug-2016 Version number: 1

used to guide insulin dose-titration for optimal glycemic control and the SMPG profiles will be collected for study analyses.

During Week 15, patients will wear a blinded CGM device for 7 consecutive days to generate minimum 4 days of useable CGM data. If a patient fails the first attempt for any reason, he/she will be retrained for CGM conduct and complete another course of blinded CGM in Week 16.

At the end of the study, the patients will be followed-up for 2 (+2) days to collect post-treatment safety information.

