8.2.1 Pharmaceutical formulation of the investigational medicinal product

The tested drug

Toujeo (insulin glargine 300 U/mL solution) is supplied for SC injection as a sterile, non-pyrogenic, clear, colorless solution in a 1.5 mL TOUJEO SoloStar disposable prefilled pen (450 U/1.5 mL).

Toujeo has the same composition as the Lantus formulation 100 U/mL with adjustment of 3-times the amount of active pharmaceutical ingredient (insulin glargine) and corresponding zinc content. The higher concentration of insulin glargine in U-300 will result for the **same dose of insulin glargine in lower injection volumes** as compared with the conventional U100 basal insulin formulations.

Application of the drug is done using the pen device allowing dose settings in the range of 1-80 U with 1U increments.

The control drug

Lantus is supplied as insulin glargine solution for SC injection 100 U/mL in 3 mL cartridges assembled in a pen-injector. The SoloStar prefilled (disposable) pen will be used and it allows for a dose setting in the range of 1-80 U with minimum dose increment of 1 U.

Note: Mixing of insulin glargine (either U-300 or U-100) with other insulins is not allowed nor dilution.

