8.2.5 Adjustment of IMP

After randomization, dose of Toujeo or Lantus will be titrated in dose steps outlined in Table 1 to achieve glycemic targets without hypoglycemia. The upward dose titration should continue until the patient reaches the target fasting (pre-breakfast/pre-injection) SMPG. ALL efforts should be made to reach the target ranges for plasma glucose by 6 to 8 weeks post randomization. Thereafter, the dose will be adjusted as necessary to maintain the glycemic control until the end of Week 14, after which, dose of Toujeo or Lantus should be **unchanged** during the CGM collection (Week 15 - 16) except in the case of dose reduction for safety reasons, eg, a basal insulin associated severe hypoglycemia.

The target range for fasting (pre-breakfast/pre-injection) plasma glucose is 80-100 mg/dL (4.4 and 5.6 mmol/L), inclusive.

As recommended in Table 1, changes in the Toujeo or Lantus dose are based on the average fasting pre-breakfast SMPG values of past 3 days measured by the patients. Other pre-prandial (pre-lunch, pre-dinner) SMPG measurements may also be taken into account.

If considered as helpful to achieve the fasting glycemic target by the investigator, the mealtime insulin (including bedtime) may be titrated before additional basal-insulin titration to achieve a bedtime and pre-breakfast glucose delta <50 mg/dL.

Table 1 - Titration of IMP dose

Mean fasting SMPG values (prebreakfast) from preceding 3 days	Insulin glargine (U-100 and U-300) dose adjustments (U/day)
>120 mg/dL (6.7 mmol/L)	+ 4 U, or split to 2 x 2 U
>100 and ≤120 mg/dL (5.6 and 6.7 mmol/L)	+ 2 U or split to 2 x 1 U
≥ 80 and ≤100 mg/dL (4.4 and 5.6 mmol/L)	No change
≥60 and <80 mg/dL (3.3 and 4.4 mmol/L)	- 2 U
<60 mg/dL (3.3 mmol/L) or occurrence of 2 (or more) symptomatic hypoglycemic episodes or one severe hypoglycemic episode (requiring assistance) documented in the preceding week.	- 2 to -4 U or at the discretion of the investigator or medically qualified designee

Good clinical judgment is to be exercised while titrating the basal insulin dose.

Regular self-monitoring of plasma glucose is very important in order to achieve the blood glucose targets. It is recommended to perform daily fasting/pre-breakfast SMPG and 5-point profiles (Section 10.2.3.1) to support the titration process. More frequent SMPG at other time-point (eg, post-breakfast and post-dinner) may be needed at the investigator's discretion.

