Patients will be familiarized with the adjustment schedule so that they will be able to monitor the dose adjustment with the assistance of the investigator or medically qualified designee. During the study, weekly contacts between the investigator and patient are scheduled to assess the response to treatment and to decide on dose adjustment. During these visits (phone or onsite), patients will report their SMPG data, insulin doses and hypoglycemia to the study site.

If needed, additional contacts will be made available for patients to discuss dose adjustments inbetween the scheduled visits. It is at the discretion of the investigator to allow well-trained patients to make their IMP insulin dose adjustments in between the scheduled visits without prior consultation of the site personnel.

Dose adjustment in cases of hypoglycemia:

- Upward titration is to be stopped for 1 week after a case of severe hypoglycemia (requiring assistance) or ≥ two episodes of documented symptomatic hypoglycemia within a week, unless there was a manageable factor (eg, omission of a meal or overdosed insulin) for the event,
- Doses of basal insulin or meal-time insulin may be reduced or modified at any time for hypoglycemia during the study,
- Small decreases of the insulin dose (eg, 1 unit) are at the discretion of the investigator or medically qualified designee, if SMPG is below 80 mg/dL (4.4 mmol/L) or if relevant hypoglycemia occurs,
- Patients who experienced mild to moderate hypoglycemia as a result of a missed meal, unusual exercise or alcohol use will be counseled on the correction of those behaviors and should not reduce their insulin dose.

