All patients are asked to self-titrate their IMP (Toujeo or Lantus) according to the algorithm provided (Section 8.2.5). The short-acting insulin analog will be continued for mealtime insulin requirements and correction of SMPG according to recommendation (Section 8.3.1). Investigators and their study staff are required to offer adequate training, thus enabling patients to successfully self-titrate their insulins.

Patients who fail to provide at least 4 days of qualified CGM data will be retrained and will repeat the CGM performance for another week (Section 10.2.4.2). **Randomization will be delayed accordingly**.

For a complete list of procedures scheduled for each study visit please refer to the Study flowchart (Section 1.2).

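### The synopsis caps each upward basal insulin step at 10% of the daily dose; Section 8.2.5 and Table 1 have no cap, and nothing says which governs.

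*Protocol*

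**What the plan says.** **Synopsis, Dose regimen.** Each titration step is limited: "the insulin dose increment should not exceed 10% of the existing glargine daily dose, irrespective of the mean fasting SMPG values". The worked example is 3 U for a patient on 30 U/day whose mean fasting SMPG exceeds 120 mg/dL. The synopsis table beside it prints steps of 4 U and 2 U, and the cap applies on top of them. The synopsis study-design text sends basal titration to this dose-regimen section.

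**Section 8.2.5 and Table 1.** Above 120 mg/dL the step is an increase of "4 U, or split to 2 x 2 U"; above 100 and up to 120 mg/dL it is 2 U, with a split into 2 x 1 U as the alternative. There is no percentage limit in the text, in the table, or in the hypoglycemia rules that follow it.

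**Which text is operative.** Section 6.1 says "Appropriate dose titration of basal and mealtime insulin will be conducted as specified in Section 8". Section 10.1.2 says "All patients are asked to self-titrate their IMP (Toujeo or Lantus) according to the algorithm provided (Section 8.2.5"). Section 8.2.5 lets the investigator "allow well-trained patients to make their IMP insulin dose adjustments in between the scheduled visits without prior consultation of the site personnel". The SAP repeats neither version, and neither document contains a precedence clause.

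**Two smaller differences.** The synopsis footnote reads "Prior to additional basal insulin titration, mealtime insulin should be titrated to achieve a bedtime and pre-breakfast glucose delta <50 mg/dL", whereas under Section 8.2.5 mealtime insulin "may be titrated before additional basal-insulin titration". Only Table 1 ties the hypoglycemia trigger for a dose reduction to events in the preceding week.

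**The concern.** A site or patient working from Table 1 can take a step that the synopsis example rules out. Three things depend on it.

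- **Safety during titration (to Week 14).** Exclusion E16 removes anyone without a documented symptomatic or severe hypoglycemic event in the month before screening, so every eligible patient has a recent event. Some patients adjust doses without first speaking to the site. The size of an upward insulin step should not depend on which page was read.
- **The key secondary endpoint.** Section 11.1 counts nocturnal symptomatic hypoglycemia from randomization onward, so the titration weeks contribute events. With about 100 sites, different readings would add avoidable variation in titration speed.
- **Compliance.** Protocol Section 11.4.1.2 and SAP Section 2.4.3.2 summarize above-planned and under-planned dosing relative to what the protocol requires. A +4 U step at 30 U/day follows Table 1 but could be classed as above-planned under the synopsis.

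**Working it through.** **Inputs.** The cap is 10% of the current daily dose (synopsis). The steps are +4 U above 120 mg/dL and +2 U above 100 and up to 120 mg/dL (Table 1). The pen is described in Section 8.2.1 as "allowing dose settings in the range of 1-80 U with 1U increments", and the Lantus pen has the same 1 U minimum. The entry dose may not exceed 80 U/day (E20); no lower limit is stated.

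**The plan's own example.** 0.10 x 30 U = 3 U, which reproduces the synopsis figure. Table 1 gives the same patient 4 U, and 4/30 = 13.3% of the dose.

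**Where the rules part.** A fixed step exceeds the cap when the dose is below step / 0.10.

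- +4 U: 4 / 0.10 = 40 U/day
- +2 U: 2 / 0.10 = 20 U/day
- 1 U: 1 / 0.10 = 10 U/day

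| Daily dose (U) | 10% cap (U) | +4 U as % of dose | +2 U as % of dose |
|---|---|---|---|
| 10 | 1.0 | 40.0 | 20.0 |
| 15 | 1.5 | 26.7 | 13.3 |
| 20 | 2.0 | 20.0 | 10.0 |
| 30 | 3.0 | 13.3 | 6.7 |
| 40 | 4.0 | 10.0 | 5.0 |

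**The split option.** The protocol does not define it. If it means two separate steps, each 2 U step still exceeds the cap below 20 U/day, and each 1 U step exceeds it below 10 U/day.

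**Very low doses.** Below 10 U/day the cap is less than 1 U (for example 0.10 x 8 = 0.8 U), which is smaller than the pen can deliver. Read literally, the synopsis then allows no increase, while Table 1 does.

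**Three successive steps above 120 mg/dL.** This assumes single steps and a cap rounded down to whole units; the protocol states no rounding rule.

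- From 20 U/day: Table 1 gives 24, 28, 32 U (+60%); the cap gives 22, 24, 26 U (+30%).
- From 30 U/day: Table 1 gives 34, 38, 42 U (+40%); the cap gives 33, 36, 39 U (+30%).

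Without rounding, the capped doses after three steps are 20 x 1.1³ = 26.6 U and 30 x 1.1³ = 39.9 U. The gaps to Table 1 are then 5.4 U and 2.1 U, instead of 6 U and 3 U.

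**The case against.** The strongest reply is that this is an omission, not a contradiction. The synopsis prints the same 4 U and 2 U steps next to the cap, so fixed steps and a cap can coexist, and Section 8.2.5 is merely silent. Both texts are worded as recommendations, and Section 8.2.5 calls for clinical judgment. This reading fails on the synopsis example: at 30 U/day and above 120 mg/dL, Table 1 followed as written gives 4 U where the synopsis says 3 U. An appeal to judgment supplies no limit and does not reconcile the two.

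Several other points stand and limit the concern.

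- The fasting target is the same in both versions, so the cap mainly changes the speed of titration.
- Section 8.2.5 provides weekly contacts, a one-week halt to upward titration after severe or repeated hypoglycemia (unless a manageable factor explains the event), and dose reduction at any time. The halt acts only after events have occurred.
- Self-adjustment between visits is for well-trained patients and at the investigator's discretion.
- The compliance consequence is an inference. Neither document says that the planned dose is derived from the titration algorithm, and overall compliance counts days with any administration, which step size cannot change.
- The titration sheet that patients receive is not in the documents, so whether the cap reaches them is unknown.

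**Conclusion.** The concern holds and must be fixed. The protocol carries two current, incompatible limits on the upward basal step. They differ below 40 U/day (+4 U step) and below 20 U/day (+2 U step) on the single-step reading. If splitting means separate steps, they differ below 20 and 10 U/day respectively. At 40 U/day and above they agree.

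The thresholds follow directly from the stated rules. The three-step illustration depends on the assumptions named with it. The number of patients affected and the effect on any endpoint cannot be estimated from the documents. The conflict does not by itself favour either arm, and the primary CGM endpoint is measured after basal titration ends. The rating rests on the cap conflict alone, because it concerns insulin dosing safety. The mealtime-insulin and preceding-week differences are supporting only. No view is taken here on which rule is right.

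**What to change.** The sponsor must reconcile the synopsis with Section 8.2.5 and Table 1, choose one basal titration rule, and state it identically in the synopsis, the body and any patient materials. The reconciled text should say:

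- whether a percentage cap applies and, if so, how it is rounded and what happens when it falls below 1 U;
- what the split option means;
- whether titrating mealtime insulin first is required or optional;
- what time window applies to the hypoglycemia trigger for a dose reduction.

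Above-planned and under-planned dosing should then be defined against that one rule in Protocol Section 11.4.1.2 and SAP Section 2.4.3.2.

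The same clarification can settle some editorial points:

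- the reduction in the lowest SMPG row (4 U in the synopsis, 2 to 4 U in Table 1);
- the two mmol/L conversions of the 130-180 mg/dL postprandial target (7.2-10 in the synopsis, 7.2-8.9 in Section 8.3.1);
- the footnote about values above target that is attached to the dose-decrease columns of the mealtime tables;
- the synopsis row boundaries at exactly 100 and 120 mg/dL, which appear to overlap but may only reflect how the PDF was read.

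The cost is one protocol clarification or amendment and a site letter, with no new procedures, visits or patients.
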